#### Statistical analyses

All statistical analyses will be conducted on an intention-to-treat basis, with patients analysed according to their assigned treatment arms, except for cases lost to follow up or withdrawal of informed consent. In addition, a per-protocol analysis will be conducted. Variables will be expressed as counts and percentages, means and standard deviations (SD), or medians and interquartile ranges (IQR) whenever appropriate.

The primary and secondary outcomes will be assessed using a two–sided superiority hypothesis test with a significance level of 0.05 and presented with a two–sided 95% confidence interval. In addition to the unadjusted *p* values for secondary outcomes, a Holm–Bonferroni procedure will be applied to control for multiple testing. Analyses will be performed using the software R (R Core Team, 2016, Vienna, Austria). A list of proposed tables and figures is in **Table 2**.

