#### Primary outcome

The effect of 'individualized high PEEP' compared to low PEEP of the incidence of PPC will be assessed using a mixed-effect generalized linear model with binomial distribution and identity link, with sites included as random effects to

account for the clustering effect and reported as absolute difference with a twosided 95% confidence interval. Results will be presented in a table of outcomes (**Table 7**). To support interpretation, a confidence distribution for the primary outcome using a normal approximation on the estimated absolute difference will be calculated. The confidence distribution will be computed to provide the frequentist probability that the absolute difference is less than 0. In addition, the confidence distribution will be reported in a plot.

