#### Other exploratory analyses

Since the primary outcome of the present study is a composite one, the choice of the statistical method is an important part of designing because various methods provide different power, depending on the situation. In addition to the standard analysis described above, the following analyses will be performed:

- Count analysis: the number of positive component events (i.e., 'count') across the composite will be assessed; the groups will be compared on the count using a Wilcoxon rank sum test, and the odds ratio with the 95% confidence interval will be assessed with a proportional odds logistic regression model;
- Individual component analysis: the effect of the intervention in each component will be analyzed estimating the risk ratio and confidence intervals with Wald's likelihood ratio approximation test using a Bonferroni correction for multiple comparisons; the 99.5% Bonferroni–corrected confidence intervals will be reported (1 0.05/10 = 0.995);

- Common effect test: a multivariate (i.e., multiple outcomes per subject) generalized estimating equations (GEE) model will be used to estimate a common effect odds ratio across the components;
- Average relative effect test: the average relative effect test will be assessed by averaging the component-specific treatment effect from the distinct effects model, and testing whether the average is equal to zero. In the GEE distinct effect model a distinct treatment effect is estimated for each component; and
- Heterogeneity of treatment effect: heterogeneity of treatment effect across components will be assessed by a treatment-by-component interaction test in the distinct effects GEE model.

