# Table 2 – List of proposed tables and figures

|               | Description   |
|---------------|---|
| Main paper    |   |
| Table 1       | Baseline Characteristics of the Included Patients   |
| Table 2       | Ventilation and Intraoperative Characteristics  |
| Table 3       | Primary and Secondary Outcomes  |
| Figure 1      | Participant Flow Diagram  |
| Figure 2      | Postoperative Pulmonary Complications in Prespecified Subgroups
A forest plot showing the absolute difference and two-sided 95% confidence intervals with p value for interaction calculated via a test for treatment-by-subgroup interaction in
the regression model. A solid line of reference in the number 1 and a dashed line of reference in the overall effect will be shown.  |
| Online Supple | ement   |
| eTable 1      | Rate of Missing Data A table showing the rate of missing data.  |
| eTable 2      | Additional Intraoperative Characteristics
A table showing additional intraoperative characteristics.   |
| eTable 3      | Rescue Therapies in Included Patients
A table showing the steps of rescue therapies in patients receiving rescue in each arm.  |
| eTable 4      | Protocol Deviations
A table reporting the protocol deviations in each arm.   |
| eTable 5      | Daily Assessment of Included Patients
A table showing characteristics over the first 5 days of follow-up.  |
| eTable 6      | Multiplicity adjustment for secondary outcome analyses
A table showing the observed p values for all the secondary outcomes and ordered from the lower until the higher and the corrected p values using a Holm–Bonferroni correction  |
| eTable 7      | Sensitivity Analyses for the Primary Outcome
A table showing the proposed sensitivity analyses for the primary outcome (count analysis, common effect test, average relative effect test and heterogeneity of treatment effect)  |

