|           | with a reduced incidence of PPC (to any extent) compared with Low PEEP is XX.X%.
B, The cumulative confidence distribution of the estimated absolute difference, with the y-axis corresponding to the confidence the absolute difference is less than or equal to
the value on the x-axis. The blue-gray area indicates a beneficial intervention (i.e., absolute difference lower than 0). The dashed vertical line indicates the median.  |
| eFigure 7 | Results of the Sensitivity Analyses for the Primary Outcome
Forest plot reporting the results of all sensitivity analyses  |

|   | Individualized High PEEP |            |
|---|--------------------------|------------|
| Age years                               | (11 - XXX)               | (11 - ^^^) |
| Age > 65 years $-$ no (%)               |                          |            |
| Male gender $-$ no (%)                  |                          |            |
| Weight kilograms                        |                          |            |
| Body mass index $ka/m^2$                |                          |            |
| Body mass index $\ge 30 \text{ kg/m}^2$ |                          |            |
| ARISCAT score                           |                          |            |
| ARISCAT > 45 - no (%)                   |                          |            |
| ASA physical status- no (%)             |                          |            |
| 1                                       |                          |            |
| 2                                       |                          |            |
| - 3                                     |                          |            |
| 4                                       |                          |            |
| Functional status – no. (%)             |                          |            |
| Independent                             |                          |            |
| Partially dependent                     |                          |            |
| Totally dependent                       |                          |            |
| Co-existing disorders – no. (%)         |                          |            |
| Diabetes                                |                          |            |
| Coronary artery disease                 |                          |            |
| COPD                                    |                          |            |

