# Table 6 (eTable 3) – Daily Assessment of Included Patients

Data are median (quartile 25th - quartile 75th) or N / total (%).

Abbreviations: PEEP is positive end-expiratory pressure, ICU is intensive care unit, VAS is visual analogue scale, SpO2 is pulse oximetry.

| Table 7 | (Table 3) | ) – Primary | and Secondary | outcomes |
|---------|-----------|-------------|---------------|----------|
|---------|-----------|-------------|---------------|----------|

|  | Individualized
High PEEP
( n = XXX) | Low PEEP
(n = XXX) | Absolute Difference
(95% Cl) | p value |
|--|--|-----------------------|---------------------------------|---------|
| Primary outcome                                      |  |                       |                                 |         |
| Postoperative pulmonary complications – no. (%)      |  |                       |                                 |         |
| Severe respiratory failure                           |  |                       |                                 |         |
| Bronchospasm   |  |                       |                                 |         |
| Suspected pulmonary infection                        |  |                       |                                 |         |
| Pulmonary infiltrates                                |  |                       |                                 |         |
| Aspiration pneumonitis                               |  |                       |                                 |         |
| Atelectasis  |  |                       |                                 |         |
| Acute respiratory distress syndrome                  |  |                       |                                 |         |
| Pleural effusion                                     |  |                       |                                 |         |
| Cardiopulmonary edema                                |  |                       |                                 |         |
| Pneumothorax   |  |                       |                                 |         |
| Secondary outcomes                                   |  |                       |                                 |         |
| Mild respiratory failure – no. (%)                   |  |                       |                                 |         |
| Intraoperative complications – no. (%)               |  |                       |                                 |         |

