| Desaturation   |  |                       |                                 |         |
| Hypotension  |  |                       |                                 |         |
| Need for vasoactive agents                           |  |                       |                                 |         |
| New arrhythmias                                      |  |                       |                                 |         |
| Postoperative extrapulmonary complications – no. (%) |  |                       |                                 |         |
| Sepsis   |  |                       |                                 |         |
| Septic shock   |  |                       |                                 |         |
| Extrapulmonary infection                             |  |                       |                                 |         |

Anastomotic leakage Acute kidney injury Intraoperative fluid balance – no. (%) Impaired wound healing – no. (%) Unplanned admission to intensive care unit – no. (%) Intensive care unit length of stay, days Hospital length of stay, days All-cause hospital mortality – no. (%)

Data are median (quartile 25th - quartile 75th) or N / total (%). Abbreviations: PEEP is positive end-expiratory pressure.

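### Does the Table 7 shell undercut the Bonferroni-corrected analysis of the ten PPC components?

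*SAP*

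**What the plan says.** The SAP deals with the ten PPC components in three kinds of place.

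- **Methods.** The individual component bullet under Other exploratory analyses fixes the effect measure: "the effect of the intervention in each component will be analyzed estimating the risk ratio and confidence intervals with Wald's likelihood ratio approximation test". The same bullet then sets the multiplicity control and the level of the intervals that are to be reported: "using a Bonferroni correction for multiple comparisons; the 99.5% Bonferroni". The Primary outcome section fits its absolute-difference model, with identity link and random site effects, to the composite. Its wording is "compared to low PEEP of the incidence of PPC will be assessed using a", and it does not mention single components.
- **Table 7 shell (Table 3 of the planned paper).** The ten components sit beneath the composite, in a table whose columns read "Absolute Difference (95% Cl") and p value. The footnote says only "Data are median (quartile 25th - quartile 75th) or N / total (%). Abbreviations: PEEP is positive end-expiratory pressure".
- **Table 2, list of displays.** eTable 7, on sensitivity analyses for the primary outcome, lists "count analysis, common effect test, average relative effect test and heterogeneity of treatment effect". That is four of the five exploratory analyses; the individual component analysis is the one not named. eFigure 7 is described as "Forest plot reporting the results of all sensitivity analyses".

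**The concern.** The text and the table shell appear to differ in three ways for the same rows: effect scale (risk ratio or absolute difference), interval level (99.5% or 95%) and multiplicity control (Bonferroni or none). The Holm–Bonferroni procedure would not help, because the SAP applies it to the secondary outcomes only.

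Table 7 is destined for the main paper, and readers turn to component rows to understand a composite. If those cells were filled in as headed, the most visible component results would be uncorrected, and the corrected risk ratios would have no display expressly assigned to them. A component could then be read as affected by the intervention when the plan's own interval does not support that.

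**Working it through.** **1. The plan's own figure.** Ten components, two-sided 5% overall: 1 − 0.05/10 = 0.995. The 99.5% level is correct. (The minus sign missing from the SAP's bracketed formula was lost when the PDF was read.)

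**2. How far the two displays differ.** The normal multipliers are 1.960 for 95% and 2.807 for 99.5%. Their ratio is 2.807/1.960 = 1.43, so on one scale the corrected interval is 1.43 times as wide. The two readings can part only for a component with an unadjusted p value between roughly 0.005 and 0.05.

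**3. Can that happen?** The SAP gives no component rates, so the rates below are assumptions. Patients per arm: 734 × 0.98 = 719. The approximation is an unadjusted normal one without site effects.

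*5% against 8%:*
- Risk difference −3.0 points; SE = √[(0.05×0.95 + 0.08×0.92)/719] = 0.0130; 95% CI −5.5 to −0.5 points; p = 0.021.
- Risk ratio 0.625; SE(log) = √[0.95/(719×0.05) + 0.92/(719×0.08)] = 0.206; 99.5% CI exp(ln 0.625 ± 2.807×0.206) = 0.35 to 1.11.
- The two displays disagree.

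*12% against 15%, the 20% relative reduction that the Sample size section assumes for the composite:*
- Risk difference −3.0 points; SE = √[(0.12×0.88 + 0.15×0.85)/719] = 0.0180; 95% CI −6.5 to 0.5 points; p about 0.10.
- Risk ratio 0.80; SE(log) = √[0.88/(719×0.12) + 0.85/(719×0.15)] = 0.134; 99.5% CI 0.55 to 1.17.
- The two displays agree.

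Disagreement is therefore possible, but the first example needs a relative reduction of 37.5%. At the planned 20%, control rates below 15% give larger p values still.

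**4. Does the plan adopt the uncorrected analysis?** The sections that prescribe an absolute difference, and what they apply it to, are:

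| SAP section | Applied to |
|---|---|
| Adherence to study interventions and ventilatory variables | ventilatory variables, vital signs |
| Other daily characteristics | daily variables |
| Primary outcome | the composite |
| Secondary outcomes | binary outcomes (median difference for continuous ones) |

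None covers a PPC component. The general sentence under Statistical analyses ("The primary and secondary outcomes will be assessed using a" two-sided 0.05 test, with a 95% interval) concerns primary and secondary outcomes. It neither extends to components nor excludes another level for them. The component bullet under Other exploratory analyses is the only rule.

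**5. How much weight can the heading bear?** The same effect and p value columns head Tables 4, 5, 6 and 7. The shells are loose elsewhere too. Table 7 labels intraoperative fluid balance as a count and percentage, although the text compares continuous outcomes by median difference. Table 6 is labelled eTable 3, while Table 2 lists the daily assessment as eTable 5. A template heading over blank cells does not replace an explicit sentence in the methods.

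**The case for a change.** The strongest case for a change is that a final SAP should not leave the content of a main-paper table open until results are known. The counts-only reading of the component rows is not stated. It is also weakened by the reference to 17 secondary outcomes: the Outcomes section numbers only nine, so some nested rows of Table 7 must be meant for testing. Even if the component rows hold counts only, the 99.5% intervals have no named table, and the one explicit list of sensitivity analyses leaves them out.

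Part of this stands. The display is unclear, and a short table note would have removed the doubt. The rest does not carry.

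- The nested rows that must be tested are secondary outcomes, for which the text authorises tests. For the primary components it authorises only the corrected risk ratio.
- Ten component risk ratios break the composite down rather than test its robustness, so leaving them out of a list of sensitivity analyses is defensible. The eFigure 7 description is wide enough to include them.
- A commitment to report made in the methods is not cancelled by a list of proposed displays.
- Family-wise error rates for ten uncorrected 5% tests would describe a procedure that no section of the SAP adopts.

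**Conclusion.** No change to the plan is needed. The mismatch is real on the page, but it is a display slip and not a conflict between two analyses. The component analysis is fully specified, correctly computed at 99.5% and labelled exploratory. An analyst who follows the text produces the corrected risk ratios and judges the components by them, whether Table 7 ends up with counts, blanks or descriptive differences in those rows. No primary, secondary or exploratory result changes, and neither do the sample size or the type I error of the primary test.

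The possible effect is confined to how a reader might take a component with p between about 0.005 and 0.05, and only if the empty cells are filled as headed and read without the methods. This conclusion assumes that the methods text governs where a table shell is silent or generic, which is the ordinary reading of an SAP. The numerical examples rest on assumed component rates.

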| Bronchospasm                              | Newly detected expiratory wheezing treated with bronchodilators.  |
| Suspected pulmonary infection             | 
 
Receiving antibiotics and meeting at least one of the following criteria: 
 
New or changed sputum;
 
New or changed lung opacities on chest radiograph when clinically indicated;
 
Tympanic temperature > 38.3 °C;
 
White blood cell count > 12,000/µL.
 
 
 
 |
| Pulmonary infiltrates                     | Any unilateral or bilateral infiltrates on chest radiography.   |
| Aspiration pneumonitis                    | Respiratory failure after the inhalation of regurgitated gastric contents.  |
| Atelectasis                               | Lung opacification with shift of the mediastinum, hilum, or
hemidiaphragm towards the affected area, and
compensatory overinflation in the adjacent non-
atelectasis lung on chest radiography.  |
| Acute respiratory distress syndrome       | According to the Berlin criteria for acute respiratory distress syndrome*.  |
| Pleural effusion                          | Blunting of the costophrenic angle, loss of the sharp
silhouette of the ipsilateral hemidiaphragm in upright
position, evidence of displacement of adjacent anatomical
structures, or (in supine position) a hazy opacity in one
hemithorax with preserved vascular shadows on chest
radiography.            |
| Cardiopulmonary edema                     | Clinical signs of congestion, including dyspnea, edema,
rales and jugular venous distention, with the chest
radiograph demonstrating increase in vascular markings
and diffuse alveolar interstitial infiltrates.  |
| Pneumothorax                              | Air in the pleural space with no vascular bed surrounding the visceral pleura on chest radiography.   |
| Mild respiratory failure                  | $PaO_2 < 60mmHg$ (or < 7.9 kPa) or SpO 2 < 90% in room air, but responding to supplemental oxygen (excluding hypoventilation).   |
| Intraoperative desaturation               | $SpO_2 \le 90\%$ or if preoperative $SpO_2 < 90\%$ an absolute decrease in $SpO_2 > 5\%$ and lasting > 1 minute.  |
| Intraoperative hypotension                | Decrease in mean arterial pressure of > 20% and lasting for > 3 minutes.  |
| Intraoperative need for vasoactive agents | Vasoactive agents more than needed to compensate for vasodilating effects of anesthesia.  |
| Intraoperative arrhythmias                | Needing intervention as suggested by the Advanced Cardiac Life Support Guidelines**.  |
| Sepsis                                    | According to SEPSIS-3 criteria***.  |
| Septic shock                              | According to SEPSIS-3 criteria***.  |
|   | vound infection plus any other infection.   |
| Acute kidney injury                       | criteria****  |

#### Table 1 – Definitions of Outcomes

\* ARDS Definition Task Force, Ranieri VM, Rubenfeld GD, et al. Acute respiratory distress syndrome: the Berlin Definition. JAMA

2012;307:2526-33. \*\* Link MS, Berkow LC, Kudenchuk PJ, et al. Part 7: Adult Advanced Cardiovascular Life Support: 2015 American Heart Association Guidelines Update for Cardiopulmonary Resuscitation and Emergency Cardiovascular Care. Circulation 2015;132:444–64. \*\*\* Singer M, Deutschman CS, Seymour CW, et al. The Third International Consensus Definitions for Sepsis and Septic Shock (Sepsis-3). JAMA 2016;315:801–10. \*\*\*\* Mehta RL, Kellum JA, Shah SV, et al. Acute Kidney Injury Network: report of an initiative to improve outcomes in acute kidney

injury. Crit Care 2007;11:R31.

# Table 2 – List of proposed tables and figures

|               | Description   |
|---------------|---|
| Main paper    |   |
| Table 1       | Baseline Characteristics of the Included Patients   |
| Table 2       | Ventilation and Intraoperative Characteristics  |
| Table 3       | Primary and Secondary Outcomes  |
| Figure 1      | Participant Flow Diagram  |
| Figure 2      | Postoperative Pulmonary Complications in Prespecified Subgroups
A forest plot showing the absolute difference and two-sided 95% confidence intervals with p value for interaction calculated via a test for treatment-by-subgroup interaction in
the regression model. A solid line of reference in the number 1 and a dashed line of reference in the overall effect will be shown.  |
| Online Supple | ement   |
| eTable 1      | Rate of Missing Data A table showing the rate of missing data.  |
| eTable 2      | Additional Intraoperative Characteristics
A table showing additional intraoperative characteristics.   |
| eTable 3      | Rescue Therapies in Included Patients
A table showing the steps of rescue therapies in patients receiving rescue in each arm.  |
| eTable 4      | Protocol Deviations
A table reporting the protocol deviations in each arm.   |
| eTable 5      | Daily Assessment of Included Patients
A table showing characteristics over the first 5 days of follow-up.  |
| eTable 6      | Multiplicity adjustment for secondary outcome analyses
A table showing the observed p values for all the secondary outcomes and ordered from the lower until the higher and the corrected p values using a Holm–Bonferroni correction  |
| eTable 7      | Sensitivity Analyses for the Primary Outcome
A table showing the proposed sensitivity analyses for the primary outcome (count analysis, common effect test, average relative effect test and heterogeneity of treatment effect)  |
| eFigure 1     | Characteristics of the Intervention
A, Line plot reporting the mean and 95% confidence interval of the driving pressure after intubation, after recruitment maneuver, during first and second hour of surgery and at the last hour by treatment group.
B, Bar plot reporting the mean difference in driving pressure between groups after intubation, after recruitment maneuver, during first and second hour of surgery and at the last hour.
C, Bar plot showing the titrated level of PEEP in the individualized high PEEP group.
D, Line plot showing the plateau pressure and driving pressure according to PEEP levels during the PEEP titration maneuver in the individualized high PEEP. |
| eFigure 2     | Level of PEEP in the Study Population
Histogram reporting the most used level of PEEP during the first five hours of the surgical procedure by treatment group.  |
| eFigure 3     | Tidal Volume, PEEP, Peak Pressure, Plateau Pressure, FiO 2 and SpO 2 During Surgery
Line graph reporting the mean and 95% confidence interval of the variables after intubation, after recruitment maneuver, during first and second hour of surgery and at the last
hour by treatment group.   |
| eFigure 4     | VAS Pain, Respiratory Rate, SpO 2 and Mean Arterial Pressure During the First Five Days of Follow-Up
Line graph reporting the mean and 95% confidence interval of the variables in the first five days of follow-up by treatment group.   |
| eFigure 5     | Patient Status in the First Five Days of Follow-Up  |

|           | Transition plot showing the status of the patients in the first five days of follow-up.   |
|-----------|---|
| eFigure 6 | Confidence Distribution for the Primary Outcome
Confidence distribution of the estimated absolute difference of the primary outcome of Individualized High PEEP versus Low PEEP constructed using a normal approximation.
A, The full confidence distribution of the estimated absolute difference, with the dashed vertical line indicating the median value and the area highlighted in tan indicating the
95% confidence interval. The orange area is related to an absolute difference greater than 0 (i.e., the intervention is associated with higher incidence of PPC vs standard care).
The dotted line at an absolute difference of 0 indicates no treatment effect. The figure demonstrates that the confidence probability that Individualized High PEEP is associated |
|           | with a reduced incidence of PPC (to any extent) compared with Low PEEP is XX.X%.
B, The cumulative confidence distribution of the estimated absolute difference, with the y-axis corresponding to the confidence the absolute difference is less than or equal to
the value on the x-axis. The blue-gray area indicates a beneficial intervention (i.e., absolute difference lower than 0). The dashed vertical line indicates the median.  |
| eFigure 7 | Results of the Sensitivity Analyses for the Primary Outcome
Forest plot reporting the results of all sensitivity analyses  |

|   | Individualized High PEEP |            |
|---|--------------------------|------------|
| Age years                               | (11 - XXX)               | (11 - ^^^) |
| Age > 65 years $-$ no (%)               |                          |            |
| Male gender $-$ no (%)                  |                          |            |
| Weight kilograms                        |                          |            |
| Body mass index $ka/m^2$                |                          |            |
| Body mass index $\ge 30 \text{ kg/m}^2$ |                          |            |
| ARISCAT score                           |                          |            |
| ARISCAT > 45 - no (%)                   |                          |            |
| ASA physical status- no (%)             |                          |            |
| 1                                       |                          |            |
| 2                                       |                          |            |
| - 3                                     |                          |            |
| 4                                       |                          |            |
| Functional status – no. (%)             |                          |            |
| Independent                             |                          |            |
| Partially dependent                     |                          |            |
| Totally dependent                       |                          |            |
| Co-existing disorders – no. (%)         |                          |            |
| Diabetes                                |                          |            |
| Coronary artery disease                 |                          |            |
| COPD                                    |                          |            |
| Smoker                                  |                          |            |
| Never                                   |                          |            |
| Former*                                 |                          |            |
| Current                                 |                          |            |
| Active cancer                           |                          |            |
| Type of surgery – no. (%)               |                          |            |
| Urgent                                  |                          |            |
| Elective                                |                          |            |
| Procedure – no. (%)**                   |                          |            |
| Gynecology                              |                          |            |
| Urology                                 |                          |            |
| Vascular                                |                          |            |
| Pancreatic                              |                          |            |
| Bowel                                   |                          |            |
| Liver                                   |                          |            |
| Gastric                                 |                          |            |
| Hepatic                                 |                          |            |
| Biliary                                 |                          |            |
| Other                                   |                          |            |
| Preoperative vital signs                |                          |            |
| Heart rate, bpm                         |                          |            |

